The general framework of CogSMART-PD is predicated on the versions that were initially designed for other neurologically impaired groups (e.g., psychosis, traumatic brain injury [TBI]). However, as PD represents a progressive disorder with its own unique set of cognitive deficits and neuropsychiatric symptoms, the program was modified substantially and tailored for use in PD. Specifically, the program includes information on cognitive and non-motor symptoms most impacted in PD as well as psychoeducation regarding the progressive nature of cognitive deficits. Likewise, strategies to improve neuropsychiatric symptoms, such as sleep, fatigue, and mood are also incorporated.

As an exploratory aim, this study will also provide information regarding the neural changes associated with cognitive training in PD. To our knowledge, only one study has attempted to use fMRI to assess changes in brain function following cognitive training. Nombela and colleagues (2011) compared the performance of 5 PD patients trained on Sudoku puzzles to 5 untrained PD patients on an fMRI executive function task. Trained individuals demonstrated improved executive function on the task as well as reduced cortical activation patterns (Nombela et al.). The authors reported that since previous studies have linked cortical over-activation in PD to the depletion of neuro-transmitters, including dopamine and their metabolites, a reduction in *overall* brain activation patterns suggest *improvement* in brain functioning. However, further study is needed to verify these findings.

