Participants: 110 patients (55 per group) with PD-MCI will be recruited for this study as well as 110 identified and consistent caregivers of the participants. All caregivers will be asked to complete several questionnaires regarding the participant's quality of life and daily functioning prior to the intervention, at follow-up visits, and after the intervention. Although attrition did not occur in Phase I, over-recruitment by 20% will be instituted to account for possible subject attrition or unusable data. Participants will receive a payment of \$40 for each of the four assessments they complete (pre- and post-intervention/support and 6- and 12-month follow-ups).

Procedures: We will primarily recruit Veterans with PD from the VASDHS Neurology and Neuropsychology Clinics. While we will attempt to exhaust recruitment at VA clinics first, recruitment of women may be limited at the VA, and therefore, we will likely need to recruit from outside clinics to obtain a PD-epidemiologically accurate gender ratio of 60 (men)/40 (women). In this regard, we will primarily recruit from the University of California, San Diego (UCSD) Movement Disorders Center. Referred participants will be screened for inclusion/exclusion criteria (please see above) and consented if appropriate. All participants will have Level II MDS-criteria based diagnosis of MCI derived from a formal neuropsychological evaluation within the past 12 months. As most participants will be referred from the VASDHS and UCSD Movement Disorder Center, the majority will have MDS-criteria MCI diagnoses prior to referral. However, should a PD patient be referred for this study who has not had formal neuropsychological testing or if testing is outdated (>12 months), pre-inclusion neuropsychological testing will be performed through [name] lab, which follows patients neuropsychologically. Likewise, if the WRAT-4 Reading scale has not been administered within the past year, this 2-5 minute measure will also be administered to ensure adequate reading level. To avoid confounds, no test proposed as outcome measures in this study will be used to determine the PD-MCI diagnosis.

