Upon meeting study criteria, participants will be randomized to one of two 10-week conditions (CogSMART-PD or Supportive Care). Randomization will occur in blocks (i.e., first 5 people enrolled will be assigned to the intervention group, next 5 will be assigned to control group, next 5 will be assigned to the intervention group, and so on until the sample size of 55 per group is met). Within one to 1.5 weeks prior to beginning the group, participants will be tested by a research assistant blinded to group assignment on a 2-2.5 hour

battery of cognitive, neuropsychiatric, health status/QoL, and strategy use measures as well as a motor assessment (UPDRS-Part III), which will immediately precede the cognitive assessment (please see Assessment/Materials). Participants will be tested in the “on-state” of parkinsonian medications to limit confounding variability (e.g., of motor symptoms, such as tremor) on test results. All participants will be tested at the same time, preferably in the morning, if possible. Breaks will be given during the assessment as needed. Groups will consist of 5 individuals with PD-MCI and be led by a trained clinician (who is not involved in the clinical care or assessment of these participants). Following the intervention and 6- and 12-months post-intervention, PD-MCI participants will be re-tested by a group-blinded research assistant. 24 months post-intervention, participants will be asked to complete a brief (15 minute) telephone interview regarding changes in health status or living situation since the 12-month follow up. Following the 12-month follow-up, the control (support) group will be permitted to join CogSMART-PD.

Assessment/Materials: Outcome measures were carefully selected so that they: 1) represent areas that are frequently impaired, dysfunctional, or problematic for individuals with PD-MCI; 2) correspond to domains that are targeted for improvement by the CogSMART-PD intervention; 3) have adequate psychometric properties for use in PD; and 4) have shown utility and applicability based on the pilot and preliminary studies. Total neuropsychological and motor testing time is estimated to be 2-2.5 hours.

Cognitive Function and Cognitive Strategy Assessment:

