Data Analysis: Preliminary analyses will begin with an examination of the distribution of variables to assess their characteristics (means, standard deviations, skewness), to provide descriptive statistics of the study population, and to allow assessment of randomization. Continuous measures will be tested for normality and homogeneity of variance. Non-normally distributed variables will be transformed to meet the normal distribution assumption for linear effects models. Analyses will include tests of randomization and comparability across conditions. Randomization will be tested by performing a series of t-tests and chi-square tests to compare the groups on demographic and initial clinical variables. Pre-specified baseline variables including age, education, gender, severity and duration of illness, and motor symptoms will be considered as potential covariates (as fixed effects) in the multivariate analyses. Any other variables (e.g., baseline cognition as assessed by the MoCA, medications) on which the groups differ initially will also be explored as covariates in subsequent analyses, as described below. In the case of missing data, appropriate data analytic techniques will be used, which may include deletion, imputation, inclusion of an indicator of missing values, or pattern-mixture modeling. Outcomes will be analyzed using SPSS release 16 (SPSS, 2007), and open source statistical software R⁸¹.

As an exploratory aim, we will recruit 60 additional individuals to complete the protocol as described above and in addition, participate in two (pre/post) hour-long brain imaging (fMRI) sessions. The imaging sessions will consist of a structural brain scanning and participation in an fMRI cognitive task (please see below). Following the baseline evaluation, half of the participants will be randomly assigned to the intervention group ($n = 30$) and participate in the CogSMART program. The groups will be broken up to consist of approximately 5 individuals. The remaining participants ($n = 30$) will be assigned to the non-intervention/control ("supportive care") group. This group will also be broken down into groups of 5 when enrolled in the intervention. Participants will be retested by a group assignment-blinded examiner on the clinical and cognitive battery and imaging protocol following the intervention or waitlist.

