Exclusion criteria: (1) Secondary causes of Parkinsonism (e.g., corticobasal degeneration, progressive supranuclear palsy, multiple systems atrophy, drug-induced parkinsonism, etc.); (2) other neurological conditions (e.g., stroke); (3) normal or dementia diagnosis via neuropsychological testing and based on the MDS criteria for PD dementia; (4) psychosis, antipsychotic treatment or treatment for substance abuse; (5) untreated current major depression disorder or anxiety disorder; (6) uncorrected vision or hearing to adequately read the manual and hear intervention facilitator; and (7) reading level below an eighth grade level determined by a standardized reading test (Wide Range Achievement Test 4 - Reading [WRAT-4]⁶⁰), as the intervention involves reading. In order not to overly restrict our sample and as almost all PD patients will be on some form of dopaminergic replacement therapy and various other medications for cognitive and mood symptoms (e.g., SSRIs), we will not exclude patients based on medications. However, we will ensure that participants are stabilized on medications by recruiting those patients who have not had any major changes in medications (i.e., PD medication regimen or antidepressant dosages) within 30 days of baseline testing and not including data in our analyses from any patient who had medication changes during the course of the treatment. We recognize that certain medications can worsen cognition, such as anticholinergic agents, amantadine, dopamine agonists and benzodiazepines⁶¹. Therefore, we will carefully document all medication types and dosages at each testing session and control for these in statistical analyses as needed. It is also recognized that medication changes may occur during and after the intervention. We will diligently record this changes and account for them in the analyses accordingly (e.g., as covariates).

There will not be any direct benefit to the caregivers, however, the investigator and associates may learn more about how participation in a cognitive skills training course impacts the function and quality of life of individuals with Parkinson's disease. Additionally, we may learn if caregivers of individuals with Parkinson's disease may benefit indirectly (e.g., improvement in caregiver's quality of life) from the group participant's (e.g., spouse, relative, friend's) participation in the intervention.

We expect no subjects once consented to fail the screening process.

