12.10a) Describe the purpose/nature of the HIPAA waiver or alteration and **list specifically, what identifiers and health information are being requested under the waiver/alteration and identify whether the waiver is for access, use, and/or collection of this information.**

1) The waiver will be used to conduct a brief phone screen on potential patients referred to the study from

outside the VASDHS as referenced in section 10.1. The phone screen will be used to determine eligibility for the study so that potential participants do not waste time traveling to the VASDHS. The data that will be collected under the waiver will include Name, address, phone number, veteran status, neurological diagnosis (if any), and the following 15 questions:

1. Are you 40 years of age or older?
2. Is English your first language?
3. Do you have any other neurological diagnosis besides PD?
4. Do you have any other neurological condition, such as stroke or traumatic brain injury?
5. Have you had DBS (deep brain stimulation) surgery? Other brain surgeries, or planned surgeries?
6. Do you have a history of memory problems, or have you been diagnosed with dementia?
7. Do you have any history of psychosis?
8. Do you have any other psychiatric history (e.g. PTSD, Bipolar Disorder, Schizophrenia, etc.)?
9. Do you have any history of major depression or anxiety (Past or current Dx)?
10. Are you currently taking any antidepressant or antipsychotic medications?
11. Have you ever been treated for substance abuse?
12. Have you ever had an acute medical crisis (major accidents, illnesses, etc.)?
13. Do you have any vision, hearing, or movement problems that could interfere with taking tests, reading, or interacting in a group setting?
14. Have you had any major changes in medications within the last month, or any anticipated within the next month?
15. Do you have a primary caregiver, spouse, relative, or close friend who would be able to answer questions about how you've been doing?

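### Phase II excludes patients whose medication changes after allocation, a nearby sentence keeps them in with adjustment, and no analysis set is defined to settle it

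*Combined protocol and SAP*

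**What the plan says.** Phase II allocates first and treats afterwards. Section 9, Phase II Procedures: "Upon meeting study criteria, participants will be randomized to one of two 10-week conditions". The primary outcome is Matrix Reasoning, assessed at 10 weeks (Section 6, Phase II, Aim 1).

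Section 10, Phase II exclusion criteria, then makes two statements about medication changes:

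- The sentence on medication stability requires no major change within 30 days of baseline testing, giving the PD regimen and antidepressant dosages as what counts as major. It goes on to promise "not including data in our analyses from any patient who had medication changes during the course of the treatment".
- Three sentences later: "It is also recognized that medication changes may occur during and after the intervention". The next sentence says the study will record these changes and "account for them in the analyses accordingly (e.g., as covariates").

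The Data Analysis part of Section 9, Phase II, mentions medications only as an example of variables "on which the groups differ initially will also be explored as covariates in subsequent analyses". It names no intention-to-treat, modified or per-protocol set. Its list of options for missing data is open and includes deletion. No other part of the supplied text defines the Phase II analysis set.

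**The concern.** The exclusion is listed with the eligibility criteria but is not one. It acts on people already allocated, because of an event during treatment, and it refers to the analyses without limit, so it reaches the primary one.

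The plan's own text makes it plausible that such changes are related to both arm and outcome. On arm, Section 7 says of CogSMART-PD that "strategies to improve neuropsychiatric symptoms, such as sleep, fatigue, and mood are also incorporated". Antidepressant dosage is one of the medication changes Section 10 treats as major, so an effect on mood could alter how often dosages change. On outcome, Section 10 itself says certain medications can worsen cognition.

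If the exclusion is applied, the contrast compares patients who stayed medication-stable on CogSMART-PD with patients who stayed medication-stable on supportive care. It no longer compares everyone allocated. If the conflict is left open, the choice between excluding and adjusting can be made after the data are seen.

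**Working it through.** **Which rule applies to whom.** Take a participant whose medication changes in week 5.

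| Statement | Treatment of that participant |
|---|---|
| Section 10, exclusion sentence | Dropped from the analyses |
| Section 10, sentences on changes during and after the intervention | Kept, with adjustment |
| Section 9, Data Analysis | Silent: medications enter only for initial group differences |

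For a change during treatment, the two Section 10 statements give different analysis sets.

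**Does screening prevent the event?** The 30-day stability rule looks back from baseline. For people referred from outside the VASDHS, phone-screen question 14 (Section 12.10a) asks: "Have you had any major changes in medications within the last month, or any anticipated within the next month". That reaches forward at most about 30 days, against 10 × 7 = 70 treatment days, and covers only changes already anticipated. Section 10 itself expects changes during the intervention.

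**Bias if the exclusion is applied.** The plan gives no figure to reproduce. Let p be the share of an arm that is excluded. Let D be the gap in mean outcome between stable patients and changers, in SD, with changers worse. The full-arm mean is (1 − p) × stable mean + p × changer mean, so

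retained mean − full-arm mean = p × D.

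The bias in the contrast (CogSMART-PD minus supportive care) is therefore

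pT × DT − pC × DC, or (pT − pC) × D when the gaps are equal.

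All rates and gaps below are assumptions.

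| pT | pC | DT | DC | Bias (SD) |
|---|---|---|---|---|
| 0.20 | 0.20 | equal | equal | 0 |
| 0.10 | 0.20 | 0.5 | 0.5 | −0.05 |
| 0.10 | 0.20 | 1.0 | 1.0 | −0.10 |
| 0.10 | 0.30 | 0.5 | 0.5 | −0.10 |
| 0.10 | 0.30 | 1.0 | 1.0 | −0.20 |
| 0.20 | 0.20 | 0.5 | 1.0 | −0.10 |

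With equal gaps, the bias favours the arm that loses more patients, so the sign reverses if CogSMART-PD has more changes. The last row shows that equal rates alone do not protect the contrast. Simulation with 2,000,000 per arm agreed (−0.050, −0.101, −0.200 and, for unequal gaps, −0.100).

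**Effect on type I error.** A second simulation assumed no true effect, 55 per arm before exclusion, and a latent correlation of 0.3 to 0.5 between medication change and worse outcome.

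| Excluded | Absolute bias (SD) | Type I error |
|---|---|---|
| 20% vs 20% | about 0 | 5% |
| 10% vs 20% | 0.05 to 0.08 | 5.6% to 6.8% |
| 10% vs 30% | 0.09 to 0.15 | 7.1% to 11.5% |

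**Precision.** The plan gives no alpha, power, effect size or SD for Phase II. Assuming a two-sample t-test at two-sided 5% with 80% power (noncentral t), the detectable differences are as follows. Section 9 (Phase II Participants) says "over-recruitment by 20% will be instituted to account for possible subject attrition or unusable data", without saying whether 110 already includes it, so both readings are shown; 55 × 1.2 = 66.

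| Start per arm | No exclusion | 10% vs 20% excluded | 10% vs 30% excluded |
|---|---|---|---|
| 55 | 0.539 SD | 50/44 left: 0.585 SD | 50/39 left: 0.605 SD |
| 66 | 0.491 SD | 59/53 left: 0.535 SD | 59/46 left: 0.556 SD |

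If the 20% comes on top of 55, a 10% versus 20% exclusion costs nothing against the 0.539 SD for 55 per arm. The bias formula does not contain sample size, so extra recruitment leaves the bias unchanged.

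**The case against.** The strongest reply is that Section 10 describes two tiers. The exclusion sentence is about stability and has just said what a major change is, so it may mean only major changes during treatment. The later sentences, which follow a remark about documenting all medication types and dosages, would then cover minor changes and changes during follow-up. This is a possible intention, but the exclusion clause carries no such limit and the later sentences expressly include the intervention period. Even if it is accepted, patients with major changes are still removed after allocation, so the main problem remains.

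A second reply is that the arms may not differ much. Both meet in groups of five for 1.5 hours weekly for 10 weeks (Section 9). Group leaders are not involved in participants' clinical care (Section 9). Section 17 expects mood and quality of life may improve under supportive care too. This stands as a caution: a large difference in rates is not shown. It does not make the rates equal, and equal rates still leave bias if the outcome gaps differ.

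Third, every magnitude here is assumed, and at 10% versus 20% the effect is modest. That is correct. The precision figures also ignore planned covariates and group delivery, and serve only to show scale.

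Finally, one could simply adopt the covariate statement. But medication change after allocation may itself be affected by arm, so adjusting the primary model for it is not neutral.

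**Conclusion.** The concern holds and should be corrected before analysis. As written, the plan removes allocated Phase II patients because of a post-allocation event, contradicts that within the same paragraph, and defines no analysis set elsewhere in the supplied text. Confidence is high about the text and the mechanism.

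Size and direction cannot be known from the documents. Under the assumed scenarios the bias formula gives 0 to 0.20 SD. The top of that range is 0.20 / 0.539 = 37% of the difference detectable with 55 per arm, and the 0.05 SD scenario is 9%. The case for change rests on who is counted in the primary contrast and on when that choice is made, not on a demonstrated large bias or on loss of power.

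**What to change.** - Remove the exclusion from the primary analysis and reconcile the two statements in Section 10.
- State in the Data Analysis part of Section 9 that the primary set is all allocated Phase II participants, analysed as allocated regardless of medication change. Use all available Matrix Reasoning scores at the 10-week assessment, and do not set an observed score to missing because medication changed.
- Do not adjust the primary model for medication change after allocation.
- Report the medication-stable subset and any medication-adjusted model as labelled sensitivity analyses, and say whether a medication change there means only the major changes described in Section 10.

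The cost is wording in two places and one or two sensitivity analyses. Section 10 already plans to document medication types and dosages at each testing session, so no new data are needed. The price is somewhat more outcome variability from medication changes. The change concerns the analysis only; no position is taken on medication management.

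### Phase II plans to adjust for medication recorded after treatment starts, which can bias the arm comparison, chiefly at 6 and 12 months

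*Combined protocol and SAP*

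**What the plan says.** Three statements in the Phase II exclusion criteria paragraph of Section 10 deal with medication in the analysis.

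- Recorded medication: the team will "carefully document all medication types and dosages at each testing session and control for these in statistical analyses as needed".
- Changes: it accepts that "medication changes may occur during and after the intervention", and continues, "We will diligently record this changes and account for them in the analyses accordingly (e.g., as covariates").
- Exclusion: stability is to be ensured partly by "not including data in our analyses from any patient who had medication changes during the course of the treatment".

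Section 9 (Phase II, Procedures) gives the timing. Allocation comes first: "Upon meeting study criteria, participants will be randomized to one of two 10-week conditions". The baseline session is described next: "Within one to 1.5 weeks prior to beginning the group, participants will be tested". Retesting follows at the end of the intervention and 6 and 12 months after it.

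Section 9 (Phase II, Data Analysis) adds that variables such as "medications) on which the groups differ initially will also be explored as covariates". Nothing there, or elsewhere in the protocol, restricts the Section 10 adjustment to baseline medication.

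**The concern.** Hypotheses 1 to 3 compare patients by assigned arm, so the target is the effect of assignment. A covariate measured after treatment starts is safe in that comparison only if the arm cannot influence it. The protocol gives reasons to doubt this here.

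- **Arm to medication.** The programme includes strategies for sleep, fatigue and mood (Section 7, Development of CogSMART-PD). Hypothesis 2 predicts greater neuropsychiatric improvement in that arm. Section 10 notes that patients take drugs for mood and cognitive symptoms.
- **Medication to outcome.** Section 10 says that several drug classes can worsen cognition.
- **Common cause.** Section 7 describes cognition in Parkinson's disease as tending to deteriorate. Decline can prompt a prescription change and also lower a test score.

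A later medication variable may therefore be a mediator, a collider, or both. Adjusting for a mediator removes part of the effect. Adjusting for a collider links arm to unmeasured prognosis, and so can create a difference where none exists. The qualifiers in the text (need, example) also leave the choice of covariates open until results are visible.

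**Working it through.** The plan states no figure on this point. The text available for review also gives no Phase II alpha, power, effect size or SD. The only design input is 55 patients per arm (Section 9, Phase II, Participants). All other inputs below are assumptions.

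**Model.** T is the arm, U is unmeasured decline (SD 1), and M is a medication change after allocation, with probability p1 in the treated arm and p0 in controls. Outcome: Y = δT + bM + eU + noise, residual SD about 1. Then

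total effect of assignment = δ + b(p1 − p0).

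The unadjusted arm difference estimates this total. The comparison of interest is the coefficient of T once M is in the model.

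**1. Mediator only.** With δ = 0.40, b = −0.5, p0 = 0.30, p1 = 0.15 and no common cause:
- total = 0.40 + (−0.5)(0.15 − 0.30) = 0.475
- adjusted = δ = 0.40
- loss = 0.075 SD, or 0.075/0.475 = 16%.

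**2. Common cause only.** True effect 0, no drug effect; decline raises the log-odds of a change by 1 per SD and lowers the score by 0.5 SD per SD. Large-sample simulation, p0 = 0.33:

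| p1 | adjusted estimate (truth 0) |
|---|---|
| 0.19 | −0.06 |
| 0.26 | −0.03 |
| 0.29 | −0.02 |
| 0.33 | 0.00 |

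**3. Both paths.** As in step 2, with δ = 0.40 and b = −0.3:

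| p0, p1 | total = 0.40 − 0.3(p1 − p0) | adjusted |
|---|---|---|
| 0.33, 0.19 | 0.442 | 0.34 |
| 0.33, 0.26 | 0.421 | 0.37 |
| 0.33, 0.29 | 0.412 | 0.38 |
| 0.33, 0.33 | 0.400 | 0.40 |

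In the first row the loss is about 0.10 SD: 0.042 from the mediator path and about 0.06 from the common cause, matching step 2.

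**4. Wider inputs.** With p0 about 0.29, p1 about 0.11, b = −0.5 and the common cause, a true 0.50 becomes 0.33 and a true 0 becomes −0.17. With b = +0.5 instead, and p1 of 0.11 or 0.18, a true 0.50 becomes 0.51 to 0.52. The direction is therefore not fixed.

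**5. Dropping patients instead of adjusting.** In the first case of step 4, excluding everyone with a change gives 0.335, against 0.330 with adjustment. The exclusion clause is no safer than the covariate.

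**6. What 0.1 SD is worth.** Power is approximately Φ(d√(n/2) − 1.96), at an assumed two-sided alpha of 0.05, with n = 55 and √27.5 = 5.244:
- d = 0.4: Φ(2.098 − 1.96) = 56%
- d = 0.3: Φ(1.573 − 1.96) = 35%
- 80% power needs about 0.53 SD.

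**7. Which rule applies when.** If the exclusion clause is followed, no change during treatment is left to adjust for at 10 weeks, so any bias there comes from the exclusion. Changes after treatment are untouched by that clause. At 6 and 12 months the covariate rule is the only handling the plan states for them. For changes during treatment the two rules cannot both apply: a patient who has been dropped cannot be adjusted for.

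**The case against.** The strongest reply is that bias requires the arm to change medication use, and the protocol never says that it does. The comparator is active: supportive care groups meet for the same 10 weekly sessions of 1.5 hours, and Section 17 expects possible mood and quality-of-life gains there too. The gap in medication changes could be small, and with equal rates the bias is zero (steps 2 and 3). The wording is also permissive, sits in an eligibility section and names no primary model. All of this stands. It limits the point to a plan that can bias the comparison; it does not make the adjustment safe.

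A reader might also infer that the Data Analysis text confines medication covariates to initial imbalance and so contradicts Section 10. It does not. It says such variables will also be explored, which adds candidates and withdraws nothing. The contradiction lies within the Section 10 paragraph, between the covariate sentence and the exclusion clause.

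The exclusion clause might be thought to make the issue moot. It does not reach changes after treatment, and it selects on a post-allocation event itself.

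**Conclusion.** The concern holds as a risk of bias. The plan states a rule that admits post-treatment medication into the outcome models, and the protocol's own account makes it plausible that both arm and decline influence that medication. The effect of assignment can then be mis-estimated, mainly in the Aim 3 analyses.

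The size is not known. The illustrative range runs from zero to about −0.06 SD at a true effect of 0, and to about 0.10 SD lost from a true 0.44 SD. Harsher inputs give more, and a favourable drug effect gives little bias or slight inflation. These figures rest on assumed change rates, drug effects and a common cause, none of which the protocol supplies.

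Two stronger readings are tempting and unsupported. One is that the plan necessarily biases the result; the documents do not show that the arm affects medication. The other is that about 23% of the effect (0.10/0.44) would be lost; that is one chosen scenario, not an estimate for this trial.

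**What to change.** In the Phase II paragraph of Section 10, replace the two covariate sentences and the analysis-exclusion clause together. If the exclusion clause stays, it would contradict the new text. Suggested wording:

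> Only medication variables recorded at or before the pre-treatment baseline session may enter the primary, Aim 2 and Aim 3 outcome models. Medication at later sessions and medication changes will be tabulated by arm. All randomized patients are analysed as allocated, whatever medication changes occur. Any analysis that adjusts for, or excludes on, post-baseline medication is a labelled sensitivity analysis or part of the mediator work (Exploratory Aim 6).

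The cut-off should be the pre-treatment session and not the moment of allocation. Section 9 describes baseline testing after randomization, so a rule tied to allocation could bar ordinary baseline medication.

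In Section 9 (Phase II, Data Analysis), state that medication covariates are baseline values only.

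The cost is wording only. Medication data are still collected and reported, with no added patients or visits.
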